- Range of motion of the PIP joint of the affected finger using a goniometer (in degrees), including any flexion contracture + Distance of fingertip from DPC
- Grip strength in the affected as well as contralateral hand using a dynamometer at Jamar 3 setting (in lbs)
- Return to activities of daily living. One question is: 'What activities can't you do?'. We also take a questionnaire to rate their ability to do certain activities (see questionnaire under this section). Patients can rate their ability to perform each activity on a scale from 1 to 5 (1 indicating no difficulty and 5 indicating unable to perform).
- VAS (a pain scale from 1 – 10, reported by the patient)
- How many oxycodone or other narcotic medications are you taking post-op? The number of pills taken will be given.
- Return to work. Patients give a date of when they started working again. Then we'll calculate the return to work in weeks
- Are you satisfied with the procedure, and would you choose to have it again for a similar problem? Answered with yes or no.
- Complications (i.e., trigger finger recurrence, infection, bleeding, etc.)

ADL questionnaire

Mass General Brigham Institutional Review Board
Intervention/Interaction Detailed Protocol

Opening jar	1	2	3	4	5
Driving	1	2	3	4	5
Household Chores	1	2	3	4	5
Carrying Groceries	1	2	3	4	5
Buttoning	1	2	3	4	5
Bathing	1	2	3	4	5
Cooking	1	2	3	4	5
Writing	1	2	3	4	5
Dressing	1	2	3	4	5
Shopping	1	2	3	4	5
Holding a book	1	2	3	4	5
Eating	1	2	3	4	5
Using a Computer	1	2	3	4	5
Holding a Phone	1	2	3	4	5
Using Toilet	1	2	3	4	5

Description of plans for return of research results as applicable

Not applicable

Definition of primary and secondary outcomes/endpoints

Primary endpoints:

- The 5 questions asked in the section above, together with the *ADL questionnaire*
- Recurrence of trigger finger or incomplete release

Secondary endpoints:

- Range of motion of the PIP joint of the affected finger (including noting any flexion contracture)
- Distance fingertip to distal palmar crease
- Grip strength in the affected hand
- Other complications than recurrence of trigger finger or incomplete release

Local site restrictions or site-specific procedures as applicable

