The visits during the first 3 months are part of standard care. Patients with persistent problems will be seen at the 6-month follow-up as part of standard care. If they are doing well clinically, we will only contact them by phone or email to complete these questionnaires using Redcap (see above for the scheme).

Remuneration as applicable

There is no remuneration for this study.

2. Risks and Discomforts

Trigger finger release is a standard procedure (whether it is open or ultrasound-guided) for a trigger finger.

This study's foreseeable risks and discomforts include the time required to complete the measurements and questionnaires. All electronic information (like measurements in Excel files) will be stored on

password-protected computers in a locked office that only study staff members can access. Study data of the questionnaires will be collected and maintained electronically using REDCap, a secure and HIPAA-compliant web-based application to which only study staff will have access. This limits the risk of a data and confidentiality breach, though it is a possibility.

We do not foresee additional risks for subjects participating in the study. Subjects will receive usual care, regardless of their participation. Physicians will be readily accessible for consultation should a subject experience discomfort while completing the measurements and questionnaires or at any time during the study.

3. Benefits

Patients will not receive any direct benefits from this study. However, their participation will help us to determine clinical outcomes after ultrasound-guided and open trigger finger release, which can help patients and physicians in shared decision-making. Potential benefits of ultrasound-guided trigger finger release could be a faster recovery (faster return to work) and better patient-reported aesthetics.

4. Statistical Analysis

Normally distributed continuous data will be stated as mean \pm standard deviations, non-normally distributed continuous data as medians with interquartile ranges and categorical data as frequencies and percentages.

We plan to statistically compare the postoperative clinical data of open trigger finger release to ultrasound-guided trigger finger release.

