We will use a student t-test to analyze normally distributed continuous data. When we compare data at two different time points within a group, we will use a paired student t-test. When we compare continuous data of two different groups, we will use an unpaired student t-test.

We will use a Mann-Whitney U test if the continuous data is not normally distributed.

We will use Fischer's exact test or a Chi-squared test for differences in categorical variables, depending on the number of events in the different groups.

Power analysis

We have performed a power analysis to find differences between two independent means (normally distributed) with alpha = 0.05, power = 0.80, and effect size 0.5. This would require a total sample size of 102 patients (51 in each group). If the data is non-normally distributed with the same alpha, power, and effect size, we would need a total of 106 patients (53 in each group).

This power analysis is performed for our most important primary outcomes: the 5-question and ADL questionnaires.

5. Monitoring and Quality Assurance

The full-time research coordinator and principal investigator are responsible for adherence to all IRB policies and guidelines and for the accuracy and completeness of all forms, entries, and informed consent.

Study data will be maintained in a locked filing cabinet and/or on password-protected computers. Questionnaires and self-reported responses will not become part of the subject's medical record. Hard copies of study-related data and forms will be stored in a lockable file cabinet. Only the investigators and study staff will have access to this information. Any magnetic or electronic information will be saved in password-protected computers, which only study staff members can access. REDCap, secure and HIPAA-compliant, will be used to collect all answers.

For guidance, refer to the following Partners policies:

Data and Safety Monitoring Plans and Quality Assurance

https://partnershealthcare-public.sharepoint.com/ClinicalResearch/DSMP_in_Human_Subjects_Research.pdf

Reporting Unanticipated Problems (including Adverse Events)

https://partnershealthcare-public.sharepoint.com/ClinicalResearch/Reporting_Unanticipated_Problems_including_Adverse_Events.pdf

6. Privacy and Confidentiality

- Study procedures will be conducted in a private setting
- Only data and/or specimens necessary for the conduct of the study will be collected

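### Recurrence or incomplete release is an unpowered primary endpoint with no planned confidence interval, so a non-significant test could not exclude a large excess of failed releases

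*Combined protocol and SAP*

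**What the plan says.** Under the definition of endpoints in Study Procedures there are two primary bullets. One is the five questions together with the ADL questionnaire; the other is "Recurrence of trigger finger or incomplete release".

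The Statistical Analysis section (the one numbered 4 after Benefits) describes "categorical data as frequencies and percentages". It compares groups with Fisher's "exact test or a Chi-squared test for differences in categorical variables, depending on the number of events in the different groups". It gives no threshold for choosing between the two tests and does not say whether chi-squared is continuity-corrected.

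The power analysis uses "alpha = 0.05, power = 0.80, and effect size 0.5" for a difference between two means and arrives at 51 per group, or 53 if the data are not normal. It closes: "This power analysis is performed for our most important primary outcomes: the 5-question and ADL questionnaires". For recurrence the documents give no expected rate, margin, interval or power. The Background says only that rates after ultrasound-guided release have been low.

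**The concern.** Whether the release worked is the basic effectiveness question for a newer technique, and the protocol ranks it as primary. Failures are expected to be few. With few events and about 50 patients per group, a significance test has little chance of detecting even a several-fold excess, and its p-value does not say how large an excess remains compatible with the data. Percentages show the observed split but not its uncertainty.

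The Benefits section says the results should support shared decision-making. The Background already summarises the one cited ultrasound-versus-open comparison as showing no significant difference in success rates. If this study yields another bare non-significant p-value, readers will not learn whether the data are reassuring or merely sparse.

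**Working it through.** **The plan's own sample size.** Inputs from the power analysis: alpha 0.05, power 0.80, standardised effect 0.5. With noncentral t, df = 2n - 2 and noncentrality 0.5 × √(n/2), n = 51 per group gives power 0.806 one-sided and 0.706 two-sided. The stated 51 therefore reproduces as a one-sided calculation; two-sided would need 64. The figure of 53 for non-normal data also reproduces one-sided, with Mann-Whitney efficiency 3/π. Neither calculation involves recurrence. I use 51 per group and two-sided 0.05 below, and give the one-sided results at the end.

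**Fisher p-value for 5 (ultrasound) v 1 (open), 51 per group.** With six events in total, the hypergeometric probabilities are:
- 6 v 0: C(51,6)/C(102,6) = 0.01337
- 5 v 1: C(51,5) × 51/C(102,6) = 0.08897

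Two-sided p = 2 × (0.01337 + 0.08897) = 0.205. Uncorrected chi-squared gives 0.092. With 0, 1 or 2 open failures, Fisher first falls below 0.05 at 6 v 0, 8 v 1 and 10 v 2.

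**Power.** Sum Bin(x; 51, p_US) × Bin(y; 51, p_open) over all tables with p < 0.05. The rates are assumptions.

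| Open v ultrasound | Fisher | Uncorrected chi-squared |
|---|---|---|
| 1% v 3% | 0.3% | 4.0% |
| 2% v 6% | 3.4% | 14.6% |
| 2% v 8% | 9.8% | 26.2% |
| 2% v 10% | 19.9% | 39.1% |
| 5% v 15% | 25.2% | 39.3% |
| 5% v 25% | 76% | 84% |

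At 53 per group, Fisher power for 2% v 6%, 2% v 10% and 5% v 15% is 3.8%, 21.6% and 26.8%.

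**Newcombe interval for the risk difference d (ultrasound minus open).** With Wilson limits (l, u) for each proportion:

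lower = d - √[(p₁ - l₁)² + (u₂ - p₂)²]; upper = d + √[(u₁ - p₁)² + (p₂ - l₂)²]

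For 5/51 v 1/51, the Wilson limits are 4.26% to 20.98% and 0.35% to 10.30%, and d = 9.80 - 1.96 = 7.84 points.
- Lower: 7.84 - √(5.54² + 8.34²) = -2.2
- Upper: 7.84 + √(11.18² + 1.61²) = +19.1

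Other tables, same method:
- 3 v 1: -5.3 to +14.1
- 2 v 1: -6.9 to +11.4
- 1 v 1: -8.5 to +8.5
- 0 v 0: -7.0 to +7.0

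**Choice of test.** At 51 per group, Fisher and uncorrected chi-squared fall on opposite sides of 0.05 at, for example, 4 v 0 (0.118 and 0.041), 5 v 0 (0.056 and 0.022) and 7 v 1 (0.060 and 0.027). The probability of such a table is 1.3% for 2% v 2%, 11.2% for 2% v 6% and 19.2% for 2% v 10%. The highest value among the rates tried was about 24%, for 1% v 8%.

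**One-sided 0.05.** Fisher is then significant at 5 v 0 (0.028) and 7 v 1 (0.030), but not at 4 v 0 (0.059), 6 v 1 (0.056) or 5 v 1 (0.102).

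**The case against.** Most of the case against concerns stronger readings, and much of it stands.

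- A reader might infer that the two named tests will conflict just where the counts fall. The documents do not support this. They give no recurrence rate, and under the assumed rates the tests usually agree, mostly because both are non-significant. Tying the choice to the number of events suggests the usual rule of Fisher when an expected count is below 5. That sends 4 v 0 (expected 2.0 per group) and 5 v 0 (2.5) to Fisher. With Yates correction, chi-squared gives 0.126 and 0.067 there, in line with Fisher. The missing threshold is a minor wording gap.
- A reader might infer that the plan will treat non-significance as equal effectiveness. It does not say so and makes no equivalence or non-inferiority claim. The Background sentence on the earlier comparison is an ordinary report of a test result.
- The p-value is not the only output. Percentages are planned, so a 5 v 1 split would be visible and a reader could compute an interval from it. That leaves to the reader what the primary analysis should supply.
- The protocol is open that power was calculated for the questionnaires, and very large excesses are detectable (5% v 25%). Disclosure explains why the test is weak for recurrence, but does not make a non-significant result informative.
- Adding an interval can create its own conflict. At 5 v 0 Newcombe gives +0.9 to +21.0 while Fisher gives 0.056; at 7 v 1 it gives +0.9 to +23.9 while Fisher gives 0.060. This is correct, and the plan must say which one leads.

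**Conclusion.** The point holds as a gap in the planned analysis of a primary endpoint. At 51 to 53 per group, a three- to five-fold excess from an assumed 2% base would be missed by Fisher's test in roughly four of five studies or more, and in most studies by uncorrected chi-squared. Plausible non-significant results leave upper limits of about 8 to 19 points (1 v 1 to 5 v 1), and no planned output would show this.

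The power figures rest on assumed recurrence rates, two-sided 0.05 and equal groups. The plan states neither sidedness nor a fixed ratio, and treatment follows the surgeon, so the groups may be unequal. One-sided testing moves the significance boundary by about one event and does not change the conclusion. Because the documents set no margin, whether an excess of this size matters is for the investigators to judge. The interval measures sampling error only; it does not address the lack of randomisation.

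**What to change.** In the Statistical Analysis section, add a paragraph for recurrence or incomplete release that:

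1. makes the risk difference (ultrasound minus open) with a 95% Newcombe interval the main result, alongside the counts and percentages;
2. names two-sided Fisher's exact test as the single secondary test, which also closes the missing-threshold gap;
3. states that the interval leads if it and the p-value disagree, as at 5 v 0 and 7 v 1;
4. requires any statement that recurrence is similar to quote the upper confidence limit.

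This needs no extra patients or data. The cost is one paragraph of text and a more cautious conclusion on recurrence.

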Institutional Review Board Intervention/Interaction Detailed Protocol

Principal Investigator: [name]

Project Title: Clinical and Patient-Reported Outcomes After Ultrasound-guided vs. Open Trigger Finger Release

Version Date: 6/6/2023

For Intervention/Interaction studies, submit a Detailed Protocol that includes the following sections. If information in a particular section is not applicable, omit and include the other relevant information.

1. Background and Significance

Trigger finger is initially treated conservatively. Conservative treatment options include modification of activities, painkiller administration, splinting, and corticosteroid injections (1). Open or minimally invasive surgical treatment can be considered if conservative treatment fails. Minimally invasive surgery options consist of ultrasound-guided or blind percutaneous trigger finger release.

Many studies have reported good clinical outcomes after ultrasound-guided trigger finger release, including low rates of catching or locking recurrence rates, high QuickDASH scores and high patient satisfaction (2-4).

Postoperative clinical outcomes of open surgery have been widely compared to percutaneous surgery (5-8). However, the comparison of postoperative results between ultrasound-guided and open trigger finger release has been scarcely reported. Nikolaou et al. reported that ultrasound-guided trigger finger release resulted in a significantly sooner return to normal activities and better patient-reported cosmetic outcomes than open trigger finger release (9). Success rates and mean QuickDASH scores did not differ significantly between these groups in this cohort.

The potential benefits of ultrasound-guided trigger finger release compared to open trigger finger release have yet to be investigated. This study aims to prospectively analyze patient-reported outcomes in patients undergoing open vs. ultrasound-guided trigger finger release.

2. Specific Aims and Objectives

This study aims to prospectively analyze clinical and patient-reported outcomes in patients undergoing open vs. ultrasound-guided trigger finger release. Patients will not be randomly assigned to one of these two groups; rather, they will undergo the type of trigger finger surgery that they already agreed to with their surgeon, and we will measure the outcomes. Because of this, the study does not change the patient's standard of care; we are simply looking to collect additional data points.

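### The sample sizes of 102 and 106 match only an undeclared one-sided alpha of 0.05; under a two-sided 0.05 t-test, 51 per group gives about 71% power, not 80%

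*Combined protocol and SAP*

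**What the plan says.** The Power analysis paragraph of section 4 (Statistical Analysis) describes a calculation "to find differences between two independent means (normally distributed) with alpha = 0.05, power = 0.80, and effect size 0.5". The result for normal data is: "This would require a total sample size of 102 patients (51 in each group"). For non-normal data with the same settings, "we would need a total of 106 patients (53 in each group"). The paragraph closes by tying the calculation to the main endpoints: "This power analysis is performed for our most important primary outcomes: the 5-question and ADL questionnaires".

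The tests named in the same section are the unpaired Student t-test for normal data and its rank-based substitute: "We will use a Mann-Whitney U test if the continuous data is not normally distributed".

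Neither the power paragraph nor any other part of the document says whether the tests or alpha are one-sided or two-sided. An alpha of 0.10 appears nowhere.

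**The concern.** Alpha 0.05, 80% power and d = 0.5 is a familiar combination, and a conventional two-sided t-test at those settings needs 64 per group. The stated 51 is 13 per group short, which rounding cannot explain.

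The plan's wording gives no reason to expect a one-sided test. The aim in section 2 is neutral: "This study aims to prospectively analyze clinical and patient-reported outcomes in patients undergoing open vs. ultrasound-guided trigger finger release". So is the analysis section: "We plan to statistically compare the postoperative clinical data of open trigger finger release to ultrasound-guided trigger finger release". The power paragraph itself speaks of finding differences.

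Two things are at stake. First, if the analysis is run two-sided at 0.05, the stated 80% power is not a property of the design, and a non-significant comparison would be given more weight than it can bear. Second, with sidedness left open, a result whose two-sided p-value lies between 0.05 and 0.10 (in the favoured direction) could be called significant or not, depending on a choice made after the data are seen.

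**Working it through.** **Inputs.** From the Power analysis paragraph: alpha = 0.05 (sidedness not given), power = 0.80, standardised effect d = 0.5, equal groups. No standard deviation or raw difference is given, and none is needed for a standardised effect. From the test descriptions in section 4: unpaired t-test, or Mann-Whitney for non-normal data. Assumption of this check: for the Mann-Whitney figure, the usual efficiency of 3/π = 0.955 relative to the t-test (normal parent distribution). The plan does not say which parent it used.

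**Formula, t-test.** With n per group, degrees of freedom are 2n − 2, the noncentrality is d·√(n/2), and power is the probability that a noncentral t exceeds the critical value t(1 − α) for a one-sided test or t(1 − α/2) for a two-sided one. The opposite tail of the two-sided test is negligible here.

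**Formula, Mann-Whitney.** The same, with n replaced by n × 3/π.

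**Step 1: reproduce 51 per group.** Noncentrality = 0.5 × √(51/2) = 2.525, with 100 degrees of freedom.
- One-sided 0.05: critical value 1.660, power 80.6%. At n = 50 the power is 79.9%, so 51 is the exact minimum.
- Two-sided 0.10: the same critical value, so also 51.
- Two-sided 0.05: critical value 1.984, power 70.6%.

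**Step 2: reproduce 53 per group.** Effective n = 53 × 0.955 = 50.6, and noncentrality = 0.5 × √(50.6/2) = 2.515.
- One-sided 0.05 (or two-sided 0.10): power 80.3%. At n = 52 it is just under 80% (79.6%), so 53 is the exact minimum.
- Two-sided 0.05: power 70.2%.

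Both stated sizes are therefore the exact minima under one and the same setting.

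**Step 3: what two-sided 0.05 requires.**

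| Test | Plan, per group (total) | Two-sided 0.05, 80% power | Two-sided power at the plan's size | d detectable with 80% power at the plan's size |
|---|---|---|---|---|
| t-test | 51 (102) | 64 (128) | 70.6% | 0.56 |
| Mann-Whitney, efficiency 3/π | 53 (106) | 67 (134) | 70.2% | 0.56 |

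The shortfall in the totals is 128 − 102 = 26 and 134 − 106 = 28. The miss probability for d = 0.5 by t-test is 1 − 0.706 = 0.294.

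**Step 4: could another reading rescue the figures?** The normal approximation for two-sided 0.05 gives 63 per group, so the choice of approximation does not explain 51. Two-sided 0.05 does give 51 if power is set at 0.70, but the plan states 0.80. Taken alone, 106 could arise under two-sided 0.05 with a non-normal parent of efficiency about 1.20, but 102 for the t-test could not.

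**Step 5: simulation check.** Two runs of 20,000 normal trials each gave two-sided t-test power at 51 per group of 70.5% and 70.7%, and two-sided Mann-Whitney power at 53 per group of 69.7% and 69.1%.

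**Step 6: non-normal data.** Two-sided Mann-Whitney power at 53 per group, for a shift of 0.5 standard deviations without ties, was 67% for a uniform distribution, 76% for a logistic, 85% for a Laplace and 95% for an exponential. No single figure or range can be quoted for non-normal outcomes.

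**The case against.** The best counter-argument is that nothing stated is false. Both totals reproduce exactly under a coherent setting, a one-sided 0.05 test is legitimate, and the plan never claims two-sided testing. The background supplies some reason to expect a direction: it reports an earlier comparison in which the ultrasound-guided technique had the advantage in return to activities and in cosmetic outcome, and section 3 (Benefits) says "Potential benefits of ultrasound-guided trigger finger release could be a faster recovery". On this view the defect is an undeclared assumption rather than an arithmetic error, and it moves the detectable effect only from 0.50 to 0.56.

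Part of this stands. One-sided testing is not ruled out by the text, and the 71% applies only if the tests are two-sided. The match at 53 also depends on taking a normal parent, although the plan gives that figure for non-normal data.

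It does not remove the point. A possible benefit is not a hypothesis, and no test direction is set for any endpoint, including recurrence or incomplete release, where either procedure could do worse. A one-sided test has to be declared with its direction. Without that, the natural reading of a plan to find differences is two-sided, and on that reading the stated 0.80 is wrong.

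**Conclusion.** The concern holds. With power at 0.80 and d = 0.5, the pair 102 and 106 follows from one-sided 0.05 (or two-sided 0.10), which the plan does not declare. Under two-sided 0.05, power is about 71% by t-test at 51 per group, and about 70% by Mann-Whitney at 53 per group if the parent is normal.

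These figures are for a single continuous outcome with every planned patient evaluable. They do not describe the yes/no items, such as satisfaction, or the study as a whole with its several primary endpoints and visits. Use of a one-sided test is a strong inference from two exact matches, not something the document records. The correction is needed because this is the plan's only sample-size justification and because sidedness governs how every p-value will be read.

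**What to change.** In section 4 (Statistical Analysis), add:

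> All tests are two-sided at the 0.05 level.

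In the Power analysis paragraph, remove the claim of 0.80 power together with the sentences that derive 102 and 106 from it, and replace them with:

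> With 102 patients (51 per group), a two-sided t-test at 0.05 on one continuous outcome has 71% power for d = 0.5, or 80% power for d = 0.56, before loss to follow-up. With 106 patients (53 per group), a two-sided Mann-Whitney test has about 70% power for d = 0.5 under a normal parent distribution (efficiency 3/π); for non-normal data the power depends on the distribution.

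If a one-sided test was intended, say so and give its direction in both the power paragraph and the analysis section. In either case the choice should be recorded before outcomes are compared, so that it cannot appear driven by the data.

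The cost is a few sentences and a less favourable stated power; no extra patients are needed. Should the sponsor prefer to keep 80% power for d = 0.5 with two-sided tests, the price is 128 patients by t-test, or 134 by Mann-Whitney under a normal parent.
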